#### 4.5.2. Immunogenicity Variables

In this study, the immunogenicity data are measuring the anti-drug response. A validated ECL assay will be performed on samples collected approximately within 15 minutes prior to the infusion on Day 1 and at Days 8, 15, 29, 61, 91 and 121 (with corresponding windows) for serum levels of anti-EV68-228-N antibodies. To measure ADA, anti-drug antibodies will be captured by EV68-228-N and detected with labeled EV68-228-N (e.g., biotin) followed by standard detection (e.g., streptavidin -SULFO-TAG).

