##### **3.2.2. Secondary**

After a single IV infusion of EV68-228-N:

- EV68-228-N concentrations in serum will be determined with a validated assay. The PK parameters will be estimated based on the concentration-time data, including area under the serum concentration-time curve (AUC) from time 0 to infinity ( $AUC_{0-\infty}$ ), AUC from time 0 to 48 hours post dose ( $AUC_{0-48}$ ), AUC from time 0 to the time of the last quantifiable concentration ( $AUC_{0-\text{last}}$ ), maximum observed serum concentration ( $C_{\max}$ ), time of the  $C_{\max}$  ( $T_{\max}$ ), apparent serum terminal elimination half-life ( $t_{1/2}$ ), total serum clearance (CL), and volume of distribution during the terminal phase ( $V_z$ ) calculated from serum EV68-228-N levels.
- Incidence of anti-EV68-228-N antibodies as measured by the proportion of participants with detectable anti-EV68-228-N antibodies in serum.

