### 3.3.3. Detectable Anti-Drug Antibody

There are three steps in the Meso Scale Discovery (MSD) Electrochemiluminescent (ECL) assay: screening assay, confirmatory assay, and titer assay. The screening assay will have qualitative results of negative (NEG), potential positive screening (PPS) and no recorded result (NRR).

An ADA confirmatory assay will be performed for specimens with PPS screening results. The result of the confirmatory assay is qualitative, NEG, NRR, or positive (POS).

A detectable ADA is defined when the confirmatory assay result is POS.

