## 11. IMMUNOGENICITY

The immunogenicity data, determined by a validated ADA assay (14), will be analyzed with mITT and Per-Protocol populations. The proportion of participants with positive screening assay results and positive confirmation assay results are summarized in [Table 15](#), [Table 16](#), [Table 17](#), and [Table 18](#).

A titer assay will be performed for specimens with detectable ADA (refer to Section 3.3.3 for the definition of detectable ADA). Geometric Mean Titers (GMT) of ADAs will be calculated, along with 95% CIs, for all groups, at each time point ([Table 19](#) and [Table 20](#)). Summaries will also be displayed graphically ([Figure 2](#)).

The GMT is defined as:

$$\text{GMT} = \sqrt[n]{X_1 * X_2 * \dots * X_n},$$

where the  $X_1, X_2, \dots, X_n$  are the titers for each participant at a certain time point for detectable ADAs. In practice, it is the equivalent of:  $\text{GMT} = \text{Exp}\{[\log(X_1) + \log(X_2) + \dots + \log(X_n)] / n\}$

The proportion of participants with detectable ADAs and Clopper-Pearson exact 95% CIs will also be computed over time to assess persistence of ADAs ([Table 21](#) and [Table 22](#)).

The individual ADA results, including screening result, confirmatory result and titers, will be presented in [Listing 10](#).

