**Table 18: Summary of Positive ADA Confirmation Assay Results by Time Point and Dose Cohort – Per-Protocol Population**

**Table 19: Anti-Drug Antibodies (ADA) Geometric Mean Titer (GMT) Results with 95% Confidence Intervals by Time Point and Dose Cohort – mITT Population**

Time Point	Statistic	3 mg/kg EV68-228-N	10 mg/kg EV68-228-N	30 mg/kg EV68-228-N	Placebo
Day 1, Pre Dose	N	x	x	x	x
	GMT	x.x	x.x	x.x	x.x
	95% CI	x.x, x.x	x.x, x.x	x.x, x.x	x.x, x.x
Day 8	N				
	GMT				
	95% CI				
Day 15	N				
	GMT				
	95% CI				
Day 29	N				
	GMT				
	95% CI				
Day 61	N				
	GMT				
	95% CI				
Day 91	N				
	GMT				
	95% CI				
Day 121	N				
	GMT				
	95% CI				

Note: N=Number of participants in each group in the mITT Population.

**Table 20: Anti-Drug Antibodies (ADA) Geometric Mean Titer (GMT) Results with 95% Confidence Intervals by Time Point and Dose Cohort – Per-Protocol Population**

Time Point	Statistic	3 mg/kg EV68-228-N (N=X)	10 mg/kg EV68-228-N (N=X)	30 mg/kg EV68-228-N (N=X)	Placebo (N=X)
Day 1, Pre-Dose	N	x	x	x	x
	GMT	x.x	x.x	x.x	x.x
	95% CI	x.x, x.x	x.x, x.x	x.x, x.x	x.x, x.x
Day 8	N				
	GMT				
	95% CI				
Day 15	N				
	GMT				
	95% CI				
Day 29	N				
	GMT				
	95% CI				
Day 61	N				
	GMT				
	95% CI				
Day 91	N				
	GMT				
	95% CI				
Day 121	N				
	GMT				
	95% CI				

Note: N=Number of participants in each group in the Per-Protocol Population.

**Table 21: Proportion of Participants with Detectable Anti-Drug Antibodies (ADA) with 95% Confidence Intervals by Time Point and Dose Cohort – mITT Population**

[Implementation note: the Detectable Anti-Drug Antibodies means that in the confirmatory ADA assays, the results are positive.]

Time Point	Statistics	3 mg/kg EV68-228-N	10 mg/kg EV68-228-N	30 mg/kg EV68-228-N	Placebo
Any time point	N	x	x	x	x
	n	x	x	x	x
	Proportion (95% CI)	x (x.xx, x.xx)	x (x.xx, x.xx)	x (x.xx, x.xx)	x (x.xx, x.xx)
Day 1, Pre Dose	N	x	x	x	x
	n				
	Proportion (95% CI)				
Day 8	N	x	x	x	x
	n				
	Proportion (95% CI)				
Day 15	N	x	x	x	x
	n				
	Proportion (95% CI)				
Day 29	N	x	x	x	x
	n				
	Proportion (95% CI)				
Day 61	N	x	x	x	x
	n				
	Proportion (95% CI)				
Day 121	N	x	x	x	x
	n				
	Proportion (95% CI)				

Note: N=Number of participants in each group at the time point in the mITT Population.

**Table 22: Proportion of Participants with Detectable Anti-Drug Antibodies (ADA) with 95% Confidence Intervals by Time Point and Dose Cohort – Per-Protocol Population**

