## 16.2.6 Individual Efficacy/Immunogenicity Response Data

### Listing 10: 16.2.6: Immunogenicity Response Data

[Implementation note:

For Screening Result, it could be NEG/PPS/NRR, which means Negative/Potential Positive/No Recorded Result.

For Confirmatory Result, it will report the results for samples that were potential positive in screening. Null for screening negative, NRR for screening NRR.

For Titer, reports titer results for samples that confirmed positive in confirmatory results. NULL for negative confirmatory results. NRR for NRR confirmatory results.]

Dose Cohort	Participant ID	Planned Time Point	Actual Study Day	Screening Results a	Confirmatory Results b	Titer c	Comment
				NEG	NULL	NA	
				PPS	NEG	NULL	
				PPS	POS	xxxxx	
				PPS	NRR	NRR	
				NRR	NRR	NA	

aThe ADA screening assay result could be Negative (NEG), Potential Positive (PPS), or No Recorded Result (NRR).

bThe ADA confirmatory assay was performed for those specimens with a PPS screening result. The confirmatory result could be Negative (NEG), Positive (POS), or No Result Recorded (NRR).

If screening result is NEG, then the confirmatory result is NULL. If screening result is NRR, then the confirmatory result is NRR.

cThe ADA titer assay was reported for those specimens with a POS confirmatory result. If confirmatory result is NEG, then the titer is NULL. If confirmatory result is NRR, then the titer is NRR. If the screen result was NEG or NRR, then the titer is NA.

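### Tables 21–22 count every ADA sample not confirmed positive as non-detectable whatever its drug level, although the assay format lets circulating EV68-228-N mask ADA, most readily at early visits and at 30 mg/kg

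*SAP*

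**What the plan says.** Section 3.2.2 makes ADA a secondary outcome: "Incidence of anti-EV68-228-N antibodies as measured by the proportion of participants with detectable anti-EV68-228-N antibodies in serum". Section 4.5.2 describes the assay format ("anti-drug antibodies will be captured by EV68-228-N and detected with labeled EV68-228-N") and calls the assay validated. ADA samples are taken before infusion on Day 1 and on Days 8, 15, 29, 61, 91 and 121. Section 4.5.3 schedules a drug concentration on the same post-dose days.

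The classification is fixed in Section 3.3.3. Only some samples go past screening: "An ADA confirmatory assay will be performed for specimens with PPS screening results". Then: "A detectable ADA is defined when the confirmatory assay result is POS". The footnotes to Listing 10 complete the rule: "If screening result is NEG, then the confirmatory result is NULL". The only code for an unusable result is NRR (no recorded result).

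Section 11 plans the summary: "The proportion of participants with detectable ADAs and Clopper-Pearson exact 95% CIs will also be computed over time to assess persistence of ADAs". The note to Table 21 defines the denominator: "N=Number of participants in each group at the time point in the mITT Population". Table 22 does the same for the Per-Protocol population. Nowhere does the SAP state a drug-tolerance limit, describe sample pretreatment, compare a sample's drug level with a limit, or provide an inconclusive class.

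**The concern.** An assay that captures ADA on the drug and detects it with labelled drug needs free binding sites on the antibody. Drug already in the serum occupies those sites and lowers the signal. A sample rich in drug can then read negative although ADA is present.

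Sampling starts on Day 8, when drug from a single IV dose of an antibody is still plentiful, and doses span a factor of ten. Masking would lower the reported proportion most where drug is highest. A low ADA rate at 30 mg/kg could then reflect the assay rather than low immunogenicity. A proportion that rises at later visits could reflect washout rather than late onset. Section 2.1 says the safety and PK data are to support a target dose for later trials, so a falsely reassuring ADA picture at the top dose would matter.

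**Working it through.** **The plan's own figure.** The SAP gives no operating figure for ADA detection. The only one for 10 participants is in Section 5: an 89.3% chance of at least one event when its probability is 20%. This reproduces: 1 − 0.8^10 = 0.8926.

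**Inputs from the SAP.** Doses 3, 10 and 30 mg/kg; 10 participants per active dose; six post-dose ADA visits, each with a scheduled drug concentration.

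**Inputs assumed, because the SAP does not give them.** One-compartment linear kinetics, volume V of 0.05–0.10 L/kg (central value 0.08), half-life of 14–28 days (central value 21), and a range of tolerance limits.

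**Which samples are affected.** Masking lowers the screening signal first. Most masked samples would therefore be screen-negative with a NULL confirmatory result, and some would be confirmatory-negative. Both groups fall outside the definition of detectable ADA and stay in N.

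**Direction with dose.** For a limit that both doses exceed at the start, 30 mg/kg stays above it log2(30/3) = 3.32 half-lives longer than 3 mg/kg. That is 47, 70 or 93 days for half-lives of 14, 21 or 28 days, against follow-up to Day 121.

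**Drug levels.** Level = (dose / V) × 2^(−(day − 1) / half-life), in µg/mL. Example: 30 / 0.08 × 2^(−7/21) = 298 on Day 8. With V 0.08 and half-life 21 days, levels at 3/10/30 mg/kg are about:
- Day 8: 30/99/298
- Day 29: 15/50/149
- Day 121: 0.7/2.4/7.1

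Across the whole assumed range, the 30 mg/kg level is 212–505 on Day 8 and 0.8–31 on Day 121.

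**Post-dose visits (of 6) above the limit at 3/10/30 mg/kg, V 0.08 L/kg:**

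| Assumed limit (µg/mL) | half-life 14 d | 21 d | 28 d |
|---|---|---|---|
| 10 | 2/3/4 | 3/4/5 | 3/5/6 |
| 50 | 0/2/3 | 0/2/4 | 0/3/4 |
| 100 | 0/0/2 | 0/0/3 | 0/1/3 |
| 250 | 0/0/1 | 0/0/1 | 0/0/2 |

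For limits of 10–100 µg/mL this is 2–6 visits at 30 mg/kg and 0–3 at 3 mg/kg. At the extreme of V 0.05 and half-life 28 days, the 3 mg/kg group reaches 4 visits for a limit of 10, because its Day 61 level is 13.6. In every case in the table, 30 mg/kg has at least as many visits at risk as either lower dose. A limit above about 505 µg/mL would leave no visit at risk anywhere in the assumed range.

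**Consequence with 10 participants.** Let true incidence be 20% and let a share f of true positives be masked. The expected observed incidence is 20% × (1 − f), and the chance of seeing any positive participant is 1 − (1 − 0.2(1 − f))^10.

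| f | Expected observed incidence | Chance of at least one positive |
|---|---|---|
| 0 | 20% | 89.3% |
| 25% | 15% | 80.3% |
| 50% | 10% | 65.1% |
| 75% | 5% | 40.1% |

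If all are masked, the report is 0/10 with an exact 95% interval of 0 to 30.8%. That interval makes no allowance for masking.

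**The case against.** The strongest reply is that everything turns on a number outside the SAP. Drug tolerance and sample pretreatment normally sit in the assay's validation documents. The SAP calls the assay validated and cites guidance on ADA assay validation. The outcome is worded as detectable antibody and defined operationally, so the SAP does not claim that a negative is a true negative. No dose comparison of ADA is specified. Much of this stands: the limit itself may properly live elsewhere, and no bias has been shown. But the classification rule, the denominator and the table shells are SAP content, and this SAP fixes them without reference to drug level. Validation alone does not say how to count a sample whose drug level exceeds the validated limit.

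A second reply is that the plan already softens the problem. Sampling runs to Day 121, and Tables 21–22 have an any-time-point row, so persistent ADA can still be caught after washout. Listing 10 can also be read against the individual concentrations in Table 77 and Listing 25. This stands for cumulative incidence, provided ADA persists. It does not protect the early by-visit proportions or the reading of persistence. The Table 21–22 shells also have no Day 91 row, which removes one of the later, lower-drug visits from the display.

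A reader might infer that ADA incidence at 30 mg/kg will be understated. The documents do not support that, since a high enough tolerance removes the effect. A reader might also infer that the affected samples are those negative at confirmation. By the SAP's own testing sequence, most would never reach that step.

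**Conclusion.** The point holds in conditional form. The stated rule would report a masked sample as non-detectable, and the exposure grows with dose and is greatest at early visits. By-visit proportions can be biased downward, and persistence can be confounded with washout. Cumulative incidence is less affected.

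The size cannot be fixed from the SAP. The counts of 2–6 visits at 30 mg/kg and 0–3 at 3 mg/kg rest on an assumed tolerance of 10–100 µg/mL, a half-life of 14–28 days, a volume of 0.08 L/kg and linear kinetics. Section 5 does not rely on dose proportionality. The direction needs only that drug levels rise with dose, but the counts would change. The outcome is secondary and descriptive, and the primary safety outcomes are untouched. The correction is worthwhile because the same-visit drug concentrations are already planned.

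**What to change.** - Cite the assay's validated drug-tolerance limit in Section 3.3.3 or 11. That such a limit is on file is inferred from the word validated and must be confirmed with the laboratory.
- Flag as inconclusive any post-dose sample that is negative at screening or confirmation and whose same-visit EV68-228-N concentration exceeds the limit. Show the flag in Listing 10 and the number inconclusive as an added row in Tables 21–22.
- Keep the planned proportion, with inconclusive samples counted as negative, as the lower bound. Add an upper bound with them counted as positive. Do not drop them from the denominator: positives would stay while negatives left, which biases incidence upward. With 1 positive and 9 inconclusive, for example, the result would be 1/1; with none positive and 10 inconclusive, it would be 0/0.
- In the any-time-point row, class a participant as positive if any post-dose sample is POS, as inconclusive if none is POS and every post-dose negative is inconclusive, and otherwise as negative. Transient ADA that fades before washout would still be missed here; the by-visit bounds show that uncertainty.
- Tables 17–20 need no change.

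The cost is SAP wording, one listing column and a few table rows, with no new samples; the rule should be set before unblinding. The downside is a wide range between bounds at early visits in the high-dose group. If none of 10 is positive and all 10 are inconclusive, the bounds run from 0/10 to 10/10.

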#### 4.5.3. Pharmacokinetic Variables

Serum EV68-228-N concentrations: The MSD ECL assay will be performed on samples collected approximately 15 minutes prior to infusion; at end of infusion (+5 minute window); 1-, 3-, and 5-hours after end of infusion, within a  $\pm$ 15 minute window; 24 and 48-hours after the end of the infusion (within a  $\pm$ 3-hour window) and on Days 8, 15, 29, 61, 91, and 121 (within  $\pm$ 1-, 2-, 3-, 7-, 14-, and 14-day window, respectively). An EV68-228-N anti-idiotype antibody will be used in the assay to capture EV68-228-N and this will be detected with an anti-Human IgG (Fc)-biotin antibody, secondary detection is Streptavidin SULFO-TAG.

PK parameters will be estimated based on the time-concentration data through a non-compartmental analysis. Estimated total serum PK parameters will include the following:

- $AUC_{0-\infty}$ : Area under the concentration time-curve from time 0 extrapolated to infinity
- $AUC_{0-\text{last}}$ : Area under the concentration time-curve from time 0 to the last concentration above the lower limit of quantitation
- $AUC_{0-48}$ : Area under the concentration time-curve from time 0 to 48hrs
- $C_{\max}$ : Maximum concentration
- $T_{\max}$ : Time of maximum concentration
- $t_{1/2}$ : Apparent terminal elimination half-life
- $CL$ : Total serum clearance
- $V_z$ : Volume of Distribution during terminal phase

Refer to Section [3.3.4](#) for parameter definition.

## 5. SAMPLE SIZE CONSIDERATIONS

As a Phase 1, first-in-human study, the number of participants was chosen principally on feasibility and using a 5:1 randomization scheme. Thus, three cohorts of 10 participants each (n=30) and 6 placebo recipients (total N=36) are proposed. With 10 participants in each cohort receiving study product, the chance of observing at least one AE of probability 20% or more is approximately 89.3% (see [Table 3](#)). Therefore, if no AEs of a given type occur in an active dose group, we can be relatively confident that they will occur in fewer than 20% of people once the treatment is implemented.

PK parameters are not a primary outcome of the study, so it has not been powered for this, however with a sample size of 10 participants per dose level, assuming the pharmacokinetics are not dose proportional, a parameter with a coefficient of variation of 120% or less has a 90% chance to be observed within 80% and 120% of the geometric mean.

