## 2.1. Purpose of the Analyses

These analyses will assess the safety and PK of EV68-228-N after a single IV infusion in healthy adult male and female volunteers. Safety and PK data from the Phase 1 study of EV68-228-N will be used to support identification of a target dose for future efficacy trials in AFM patients.

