## 10. PHARMACOKINETICS

EV68-228-N concentrations and PK parameters will be summarized by Dose Cohort. Statistics include the arithmetic mean, median, SD, geometric mean (GM), coefficient of variation (CV), minimum, and maximum. CV will be calculated using the method for log-normally distributed data and reported as a percent:

$$CV\% = \sqrt{\exp(s^2) - 1} \times 100\%, \text{ where } s^2 \text{ is the standard deviation of the log-transformed data}$$

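### The PK precision claimed for 10 participants per dose level (90% chance of falling within 80–120% at a CV of up to 120%) is wrong: the chance is about 50%, and 90% requires a CV of about 40% or less

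*SAP*

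**What the plan says.** SAP Section 5 (Sample Size Considerations) explains that the number of participants was set mainly by feasibility and that the study is not powered for PK. It then offers a numerical assurance about PK all the same. It applies "with a sample size of 10 participants per dose level" and is made "assuming the pharmacokinetics are not dose proportional", so each dose level stands alone. Under those conditions, the claim is that any PK parameter showing a "coefficient of variation of 120% or less has a 90% chance to be observed within 80% and 120% of the geometric mean".

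No derivation is given. The only definition of the CV is in Section 10 (Pharmacokinetics): "CV will be calculated using the method for log-normally distributed data and reported as a percent", with the formula CV = √(exp(s²) − 1). Section 2.1 says that the safety and PK data "will be used to support identification of a target dose for future efficacy trials in AFM patients".

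**The concern.** A CV of 120% is very large variability for a group of 10. On a simple normal approximation the relative standard error of a mean is 120%/√10 ≈ 38%, so a ±20% band is only about half a standard error wide on each side. That cannot hold 90% of the sampling distribution.

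The sentence is the only quantitative statement in the SAP about how well the PK endpoints will be estimated, and PK is a secondary objective intended to inform later dose selection. If the figure is wrong, a reader planning from the SAP would believe that even highly variable parameters will be estimated to within 20%. The adverse-event figure in the same section is correct, so nothing signals that its neighbour is not.

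**Working it through.** **Inputs**

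- n = 10 per dose level, no pooling across doses (Section 5).
- CV = 120%, the upper end of the stated range (Section 5).
- Limits 0.80 to 1.20 times the geometric mean, stated probability 90% (Section 5).
- CV = √(exp(s²) − 1) (Section 10). Section 5 does not say which CV it means; using this one is an inference, and the alternatives are tested below.

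**A figure that reproduces.** The adverse-event probability in Section 5 is 1 − 0.8¹⁰ = 0.893, as stated.

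**The PK figure under the log-normal model**

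1. Log-scale SD: σ = √ln(1 + CV²) = √ln(2.44) = 0.944.
2. Standard error of the log geometric mean: 0.944/√10 = 0.299.
3. Limits in standard errors: ln(1.2)/0.299 = 0.610 and ln(0.8)/0.299 = −0.747.
4. Probability: Φ(0.610) − Φ(−0.747) = 50.2%. A simulation with 400,000 replicates gives 50.1%.

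The stated 90% is not reproduced. With these inputs, the central 90% range of the observed geometric mean is exp(±1.645 × 0.299), about 61% to 163% of the true value.

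**Other readings at CV 120%**

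| Reading | Chance |
|---|---|
| Geometric mean, n = 10, log-normal | 50.2% |
| Same, limits 80–125% | 54.5% |
| Same, log-scale SD taken as ln(1 + CV²), from the literal label of s² in Section 10 | 52.7% |
| Same, log-scale SD taken as 1.2 | 40.6% |
| Normal approximation, ±20%, n = 10 | 40.2% |
| Same, using the t distribution | 38.9% |
| Sample median, n = 10 | 43.6% |
| Arithmetic mean about the true arithmetic mean, n = 10 | 43.5% |
| Arithmetic mean about the true geometric mean, n = 10 | 25.0% |
| One participant's value | 17.0% |
| At least one of 10 participants within limits | 84.5% |
| Geometric mean, all 30 active participants pooled | 75.7% |
| Same, limits 80–125% | 80.4% |

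**What would give 90%**

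- At n = 10, the largest CV is 39.9% (log-normal). Check at CV 40%: σ = √ln(1.16) = 0.385, standard error 0.122, probability 89.9%. The limit is about 38% under a normal approximation and 45% with limits of 80–125%.
- At CV 120%, the required n solves to 60.4, so 61 per dose level.

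**A possible source.** Dividing the SD by n instead of √n gives 1.2/10 = 0.12, and 2Φ(0.2/0.12) − 1 = 90.4%. That matches the stated figure, but the document does not show it, and the conclusion does not depend on it.

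**The case against.** The best case for leaving the sentence alone is that nothing rests on it. Section 5 says that the sample size is a matter of feasibility and that PK is not powered. Dose escalation follows safety review, there is no interim analysis, and the primary analyses are descriptive. The PK tables will report the geometric mean, SD, range, observed CV and n for each dose level, together with individual values, so readers of the results will see the actual variability. The SAP gives no expected CV for this antibody. If it turns out at or below about 40%, the 90% is met anyway; the 50% applies only at the top of the stated range.

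All of that stands, and it limits the consequence. It does not make the sentence true: the claim covers every CV up to 120%, and fails for any above about 40%.

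The wording is also loose. It does not say what is observed, or whether the reference is the true or the sample geometric mean. The reading that comes nearest is that at least one of 10 participants falls within the limits, at 84.5% (about 87% with limits of 80–125%). That is not what the sentence naturally means, and it still is not 90%. The looseness does mean that a replacement figure should name its model.

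**Conclusion.** The concern holds. With 10 participants per dose level and a CV of 120%, the chance that the observed geometric mean lies within 80–120% of the true one is about 50%, not 90%. The CV at which 90% is reached is about 40%, so the tolerable variability is overstated by a factor of 120/40 = 3.

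The 50.2% and 39.9% assume log-normal data and the CV formula of Section 10. The conclusion does not hinge on that choice: the group-estimate readings tried at n = 10 give 25% to 55%, and the CV limit for 90% moves only between about 38% and 45% across the models tried.

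The statement is wrong as written, and it errs in the study's favour. Its reach is limited to the description of PK precision; the safety endpoints, the sample size and the planned analyses are unaffected.

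**What to change.** Replace the sentence in Section 5 with one that names the estimate, the reference and the model, for example:

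> With 10 participants per dose level, and assuming log-normally distributed values, a PK parameter with a CV of about 40% or less has a 90% chance that its observed geometric mean falls within 80% to 120% of the true geometric mean. At a CV of 120% the chance is about 50%.

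If a different model or limits of 80–125% were intended, say so and give the matching CV limit (about 38% for a normal approximation, 45% for 80–125%).

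The cost is one sentence in the SAP, and the same correction in the protocol if the figure is repeated there. No change to the sample size, analyses or tables is needed. The stated precision becomes less favourable.
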